# 1. PROTOCOL SUMMARY

#### 1.1. SYNOPSIS

**Title of Study:** A Phase 2, Open Label Study Evaluating the Safety and Efficacy of PTX-022 (sirolimus) Topical Gel 3.9% in the Treatment of Microcystic Lymphatic Malformations

Name of Sponsor/Company: Palvella Therapeutics

Name of Finished Product: PTX-022 (sirolimus) Topical Gel 3.9% w/w

Name of Active Ingredient: Sirolimus

# Objectives:

Safety Objective:

The primary objective of the study is to evaluate the safety of PTX-022.

Efficacy Objective:

The secondary objective of the study is to evaluate the effectiveness of PTX-022 in treating microcystic LM.

### Study Design and Duration:

This is an open-label study to evaluate the safety and effectiveness of PTX-022.

The study will consist of a screening and baseline period, 12-week treatment period and 4-week follow up period.

Participants will have 8 visits (remote or on-site) which include:

- Screening
- Day 1 +4 days
- Day 7 (blood draw only done remote or onsite)  $\pm$  2 days
- Day  $28 \pm 4$  days, Day  $56 \pm 4$  days, Day  $84 \pm 4$  days
- Day  $14 \pm 4$  and Day  $112 \pm 4$  (remote)

Number of Study Centers: Approximately 5 sites in the United States

Sample Size: ~10-20 subjects dosed

# **Duration of Participation:**

Each subject will participate in the study for approximately 20 weeks from the time the subject signs the ICF through the safety follow-up period.

**Duration of Study:** The study will require approximately 12 months from the beginning to the end of the study (first subject signing the ICF to last contact with last subject).

## **Screening Period Inclusion Criteria:**

Participants are eligible to participate in the screening period only if all the following inclusion criteria apply:

- 1) The participant must be at least 6 years of age.
- 2) If less <18 years of age, the participant and legal guardian must provide written informed consent/assent prior to any study procedures.
- 3) The participant must have a clinically confirmed vascular malformation which contains within it a superficial (visible on the skin) microcystic lymphatic malformation (LM).
- 4) The microcystic LM to be treated (lesion) must have a defined total area of
- 5) The participant is willing to abstain from application of other topical medications (prescription or over the counter)
- 6)
- 7) At least have elapsed since the participant has had any major surgery.
- 8) At least have elapsed since the participant has completed therapy with a Growth Factor (GF) that supports platelet, red or white cell number or function.
- 9) Participants must not have received any investigational drug or biologic within whichever is longer, prior to starting treatment with and during treatment with PTX-022.
- 11) The participant is willing to have blood collected for safety and PK testing.

# Screening Period Exclusion Criteria:

Participants are not eligible to participate in the screening period if any of the following exclusion criteria apply:

- 1) The participant has used sirolimus in the past 6 weeks.
- 2) The participant has previously participated in a clinical trial evaluating an investigational product for treatment of Vascular Anomalies, including microcystic LM in the last 3 months.
- 3) The participant has used a topical, oral, or interventional treatment that might interfere with the evaluation of the study IP. Among these are use of the following:

10)

- 4) The participant has had either COVID-19 or the COVID-19 Vaccine within the last 6 weeks.
- 5) Participants who require medications and OTC supplements that inhibit/ induce CYP3A4 activity to control concurrent medical conditions.
- 6)
- 7) Participants with known hypersensitivity to any of the ingredients in the study medication formulation.
- 8) Known history of HIV seropositivity or known immunodeficiency.
- 9)
- 10) Concurrent severe and/or uncontrolled medical disease which could compromise compliance with safety monitoring requirements for sirolimus
- 11) Participants previously treated for invasive cancer within the past 5 years unless the Investigator concludes history of cancer is not confounding to safety.
- 12)
- 13)
- 14) The participant has any condition or situation which, in the Investigator's opinion, may put the subject at significant risk, could confound the study results, or could interfere significantly with the subject's participation in the study.
- 15) Participants deemed by the investigator as unwilling or unable to remain compliant with all tests and procedures, adherence to the study drug administration regimen and other protocol-required activities.

#### **Baseline Period Inclusion Criteria**

Participants are eligible to participate in the baseline period only if all the following inclusion criteria apply:

- 1) Participant has completed the screening period
- In the Investigator's opinion, the participant's overall health status, including adequate organ function, LDL and cholesterol levels, should be appropriate to permit participation in this clinical trial.
- 3) The participant has adequate Renal Function.
  - a. eGFR>90 mL/min/1.73m^2 or CrC1>90 mL/min

#### **Baseline Period Exclusion Criteria**

Participants are not eligible to participate in the baseline period if any of the following exclusion criteria apply:

Participants deemed by the investigator as unwilling or unable to remain compliant with all tests and procedures, including adherence to the study drug administration regimen and allowing healthcare workers into the home and other protocol-required activities.

#### Open-Label Treatment Period Inclusion Criteria:

Participants are eligible to participate in the open-label treatment period only if all the following inclusion criteria apply:

1) Maintained compliance with completion of the PDD during the Baseline period.

# **Open-Label Treatment Period Exclusion Criteria:**

Participants are not eligible to participate in the open-label treatment period if any of the following exclusion criteria apply:

1) Participants deemed by the investigator as unwilling or unable to remain compliant with all tests and procedures, including adherence to the study drug administration regimen and other protocol-required activities.

# Investigational Product (IP), Dose, Route of Administration, and Regimen:

Test product: PTX-022 (sirolimus) Topical Gel 3.9% w/w

In accordance with study participant safety and tolerability, treatment will be applied according to this administration schedule:

- All subjects shall complete 12 weeks of therapy.
- PTX-022 will be topically administered each day PTX-022 should be applied once daily to the lesion area specific instructions will be available in the Participant Instruction for Use manual. If

## **Study Assessments:**

The study will be conducted as outlined in the Schedule of Assessments. For all safety and efficacy measurements, study participants and investigators will be provided with study specific training to ensure consistent evaluations.

#### Safety Assessments:

Safety will be assessed through adverse event (AE) evaluations. During the study, subjects will be assessed for the occurrence of new and ongoing AEs. Descriptions of AEs will include the dates of onset and resolution (if resolved), maximum severity, and seriousness, action taken regarding the study drug, corrective treatment, outcome, and the Investigator's assessment of causality. AEs

[figure not shown]
Amendment #4

present at any visit will be followed to resolution (return to normal or to the baseline state) or until clinically stable as determined by the Investigator.

Safety Laboratory Tests: Routine safety laboratory tests (complete blood count/differential urinalysis and serum chemistry) will be performed. Laboratory samples may be obtained from a central or local laboratory facility. Any out-of-range laboratory result that is considered clinically significant by the Investigator will be recorded as an AE and should be confirmed by repeat testing at the discretion of the Investigator. Clinically significant laboratory abnormalities at any visit will be followed to resolution (return to normal or to the baseline state) or until clinically stable as determined by the Investigator.

Physical Examinations: Investigator will evaluate body systems with trial participant.

All Adverse Events will be evaluated using Common Toxicity Criteria for Adverse Events (CTCAE) version TBD at time of final protocol.

#### **Statistical Methods:**

This is a descriptive, open-label pilot study. Primary and secondary outcomes will be reported by mean or percentage and 95% confidence interval.

All statistical processing will be performed using SAS® or R3.6.1 or later version unless otherwise stated. Summary tables (descriptive statistics and/or frequency tables) will be provided for baseline variables and safety and efficacy variables. Continuous variables will be described by descriptive statistics (n, mean, standard deviation, minimum, median, and maximum). Frequency counts and percentage of subjects within each category will be provided for categorical data.

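### Does reporting a mean or percentage with an unnamed type of 95% interval leave this 10-20 subject pilot without a sound analysis?

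*Combined protocol and SAP*

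**What the plan says.** The Synopsis, under Statistical Methods, characterises the trial plainly: "This is a descriptive, open-label pilot study". The reporting rule follows: "Primary and secondary outcomes will be reported by mean or percentage and 95% confidence interval". For scores, "Continuous variables will be described by descriptive statistics (n, mean, standard deviation, minimum, median, and maximum"; for categories, "Frequency counts and percentage of subjects within each category will be provided for categorical data". Summary tables "will be provided for baseline variables and safety and efficacy variables". No interval method is named, and change from baseline is neither required nor excluded. The text states no hypothesis test, alpha, power or target precision.

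The size is given under Study Design and Duration: "Sample Size: ~10-20 subjects dosed". The Objectives make safety primary. The secondary aim is to "evaluate the effectiveness of PTX-022 in treating microcystic LM".

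The Schedule of Assessments (Section 1.2, Table 2) places CGI-S and Overall PGI-S before dosing on Day 1 and again at Days 28, 56 and 84. DLQI is placed on Day 1 and Day 84. A footnote counts the Day 1 values as baseline. CGI-C and Overall PGI-C are scheduled at Days 28, 56 and 84.

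**The concern.** Safety is the primary objective, and with 10 to 20 subjects many adverse event categories will show no events or one. If the programmer used the textbook normal-approximation interval, an event seen in nobody would be reported as 0% with an interval of 0-0%, which suggests certainty where the data allow a sizeable true rate.

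On effectiveness there is no control arm. A mean CGI-S at Day 84 with its own interval does not show whether anyone improved; the within-subject difference from Day 1 does. If the planned mean were only a visit mean, the Day 1 scores would be collected and the pairing then ignored.

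**Working it through.** **Inputs.** n = 10 and n = 20 are the ends of the range in Study Design and Duration. The 95% level is from Statistical Methods and is taken as two-sided. True event rates of 5% and 10%, correlations r = 0.3, 0.5 and 0.7 between Day 1 and Day 84, and equal SDs at the two visits are assumptions, because the documents give no such figures. The sample size has no stated basis, so there is no figure to reproduce.

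**1. Interval when no events are seen**

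- Normal approximation, p ± 1.96√(p(1−p)/n): at p = 0 the width is zero.
- Exact (Clopper-Pearson) upper limit, 1 − 0.025^(1/n): n = 10 gives 1 − 0.692 = 30.8%; n = 20 gives 1 − 0.832 = 16.8%.
- Wilson upper limit, z²/(n + z²) with z² = 3.84: 3.84/13.84 = 27.8%; 3.84/23.84 = 16.1%.

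**2. Coverage of a nominal 95% interval**

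For n = 10 and a true rate of 10%, the normal interval misses at 0 events (zero width) and at 5 or more (5/10 gives 19.0% to 81.0%). It covers at 1 to 4 events, so coverage is P(X ≤ 4) − P(X = 0) = 0.9984 − 0.3487 = 0.650. For n = 20 and 5%, the same counts cover: 0.9974 − 0.3585 = 0.639.

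| n, true rate | Normal | Wilson | Exact |
|---|---|---|---|
| 10, 5% | 40.0% | 91.4% | 98.9% |
| 10, 10% | 65.0% | 93.0% | 98.7% |
| 20, 5% | 63.9% | 92.5% | 98.4% |
| 20, 10% | 87.6% | 95.7% | 98.9% |

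By symmetry the same values apply at 95% and 90%.

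**3. Means**

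The t interval has 95% coverage for normal data, with half-width 0.715 SD at n = 10 and 0.468 SD at n = 20. Using 1.96 with an estimated SD would cover 91.8% and 93.5%, a much smaller shortfall.

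**4. Change from baseline**

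Let s be the SD at each visit.

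- SE of the Day 84 mean: s/√n.
- SE of the difference of two visit means, treated as unpaired: s√(2/n).
- SE of the mean paired change: s√(2(1−r)/n).

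| r | Paired change / unpaired difference = √(1−r) | Paired change / Day 84 mean = √(2(1−r)) |
|---|---|---|
| 0.3 | 0.837 | 1.183 |
| 0.5 | 0.707 | 1.000 |
| 0.7 | 0.548 | 0.775 |

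The reductions of 16%, 29% and 45% in the first column are against an unpaired comparison of visits, which the text nowhere plans. Against a single-visit mean, change is no more precise until r exceeds 0.5. Its value here is that it answers the right question.

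**5. What the text commits to**

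The rule asks for "mean or percentage and 95% confidence interval" and stops there. An exact interval for 0 of 10, reported as 0-30.8%, complies fully; so does a t interval for the mean change in CGI-S. A mean, or a percentage in each category, for CGI-C or Overall PGI-C concerns change by the name of the scale. The failures in steps 1 and 2 belong to a method that the plan does not choose.

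**The case for a change.** The best case for a change is that silence is itself the defect. One sentence permits 0-0% or 0-30.8% from the same data, on the primary objective, and leaves the choice open until the data are seen. Zero counts will be common: at an assumed true rate of 5%, the chance of no events is 0.95^10 = 60% with 10 subjects and 0.95^20 = 36% with 20. Summarising baseline variables is not a paired analysis, and CGI-C and PGI-C do not supply within-subject change in CGI-S, PGI-S or DLQI. A Day 84 mean is not an estimate of change, so its precision is no argument against using the change. Two sentences would settle both matters without new data.

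Much of this stands. The synopsis does omit both details, and a normal-approximation interval at 0 of 10 would be useless. What does not stand is the step from an omission to a faulty analysis. No test, threshold or go/no-go rule depends on the interval. Counts are reported beside percentages, so a reader who sees 0 of 10 can recompute the limits. The Adverse Event Coding paragraph plans tabulation by participant and mentions no interval, and no responder endpoint is defined in the text. That the baseline goes unused is inferred only from silence: the mean of an outcome can be its mean change, and the Day 1 scores are labelled as baseline in the schedule.

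**Conclusion.** No change follows. This is a gap that a competent analyst fills sensibly: exact or Wilson limits for percentages, t limits for means, and change from Day 1 shown beside the visit values. Each fits the sentence as written and needs no data beyond those scheduled.

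The size of the problem is conditional. If normal-approximation limits were used, coverage would be about 65% at n = 10 with a true rate of 10% and about 64% at n = 20 with 5%, and zero counts would carry intervals of no width. Those rates are assumed, and nothing in the plan selects that method. The gains from pairing rest on assumed correlations and equal SDs, and they do not measure a loss in this plan.

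The conclusion rests on the synopsis and schedule, which are partly redacted and contain no endpoint definitions. It also rests on the descriptive purpose of the study. If an interval limit were to decide something, the method would have to be fixed in advance.

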# Adverse Event Coding

AEs will be coded by system-organ-class and preferred term using the most current Medical Dictionary for Regulatory Activities (MedDRA). Events will be recorded from signing of informed consent through 30 days following the last dose of PTX-022 and will be tabulated by maximum severity according to NCI-CTCAE (v.4.03). The calculation of AE incidence will be based on the number of participants per AE category. For each participant who has multiple AEs classified to the same category, that participant will be tabulated under the worst toxicity grade for that AE category. Summary tables will be presented by dose level, seriousness, severity, and relatedness.

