# 27June2022

# 1.2. SCHEDULE OF ASSESSMENTS (SOA)

### Table 2. Schedule of Assessments

	Screening	Baseline Remote	Open-Label Treatment 						
	Visit 1 Screening 		Visit 2 	Blood Draw	Phone Contact	Visit 3	Visit 4	Visit 5	follow-up  Visit 6 Phone contact
Visit Day 	Up to 6 weeks	14-28 days	Day 1	Day 7	Day 14	Day 28	Day 56	Day 84	Day 112
Informed Consent	X	3							
Eligibility Criteria	X		$X^3$						
Med History/ Demographics	X								
Physical Exam	X							X	
Height and Weight	X 							X	
Vital Signs	X		X 			X	X	X	
Clinical Laboratory Tests 	X			X 		X		X	
PK Tests		7				X	X	X	
Urine Pregnancy Test	X	9	$X^3$					X	
CGI-S		3.	$X^3$			X	X	X	
CGI-C		3				X	X	X	
Photography	X	98 9.	$X^3$			X	X	X	

<sup>1 Re-screening is permitted as described in Section 5.5.1

Confidential

<sup>2 Visit window is +/4 days for all visits during the open-label treatment period and Post-treatment follow-up period, excluding Day 1 and 7. Day 1 visit window is +4 days and Day 7 blood draw window is +/- 2 days.

<sup>3 Assessments on Day 1 of OLT should be conducted prior to application of study intervention and are considered part of Baseline

<sup>4 Height is obtained at screening only

<sup>5 Day 7 is sirolimus only and does not need to be fasting.

<sup>6 Fasting labs are required for Visit 3 and Visit 5.

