#### Protocol PALV-06 27June2022 Amendment #4

i inchanch na										
Assessment of lesion leakage										
Assessment of lesion bleeding										
Assessment of lesion impact on function										
LM Symptom Severity Scale (Pain)										
LM Symptom Severity Scale (Crusting)		√7								
PGI-SL										
PGI-SB	3									
PGI-CL										
PGI-CB										
Overall PGI-S 			√3			✓	✓	✓		
Overall PGI-C						✓	✓	✓		
DLQI			√3					√ 10		
TSQM								√ 10		
Adverse Events	$X^9$		X	X	X	X	X	X	X	
Application Site Reaction Assessment			X			X	X			
Concomitant Medications	X		X	X	X	X	X	X	X	
Dispense/Collect IP			X			X	X	X		
Accountability/Compliance	25.5		X			X	X	X		
Exit Interview									$X^{12}$	

Palvella Therapeutics, Inc.

<sup>7 Daily in the PDD

<sup>8 Weekly in the PDD

 SAEs will be captured from time of informed consent. AEs not meeting SAE criteria will be captured starting at time of first dose.

<sup>10 Collected after the PGI-S/C

  If parent is completing daily and in-person questionnaires for a child, it should be the same parent completing them throughout the course of the study.
 12 Interviews can occur any time after end of treatment. Interviews will be conducted by an independent, third party. Please refer to the Interview Guide for more information on conduct.

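### Adverse events are to be recorded for 30 days after the last dose, but the last scheduled AE contact is nominally 28 days after it

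*Combined protocol and SAP*

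**What the plan says.** Four places in the synopsis and the Schedule of Assessments bear on this point.

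- **AE window.** Under Adverse Event Coding, events are recorded from consent "through 30 days following the last dose of PTX-022". The incidence and severity tables described there are built on these events.
- **Study length.** Study Design and Duration gives a "12-week treatment period and 4-week follow up period", with the last two visits at Day 84 ± 4 and Day 112 ± 4, the latter remote. The Investigational Product section adds: "All subjects shall complete 12 weeks of therapy".
- **Last AE contact.** In Table 2 the final column is Visit 6, a phone contact at Day 112, and the Adverse Events row is marked there. Footnote 2 sets the tolerance: "Visit window is +/4 days for all visits during the open-label treatment period and Post-treatment follow-up period", with separate rules for Days 1 and 7 only.
- **Other provisions on AEs or late contact.** Under Safety Assessments, AEs "present at any visit will be followed to resolution" or until stable. Footnote 9 of the schedule sets when capture starts ("AEs not meeting SAE criteria will be captured starting at time of first dose", with serious events from consent) but gives no end. Footnote 12 allows an exit interview at any time after treatment ends: "Interviews will be conducted by an independent, third party".

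**The concern.** A 4-week follow-up is 28 days and the AE window is 30. A site that follows the schedule to the day makes its last AE enquiry before the stated window has closed, and one that uses the early side of the visit tolerance does so by a wider margin.

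Safety is the primary objective, and the AE tables are the main safety output. A new event that starts after the call and is not reported spontaneously could be missed, while the tables would be read as covering a uniform 30 days after dosing. The sample is about 10 to 20 subjects, so one subject with a missed event moves an incidence by 1/20 = 5 to 1/10 = 10 percentage points.

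**Working it through.** **Inputs**

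- AE window: last dose + 30 days (Adverse Event Coding).
- Treatment: 12 weeks; follow-up: 4 weeks (Study Design and Duration).
- Last AE contact: Day 112 ± 4, that is, Days 108 to 116 (Study Design and Duration; Table 2 and its footnote 2).
- Last dose: Day 84. This is inferred from 12 weeks of once-daily application (12 × 7 = 84). The dosing text is partly redacted and names no last-dose day.

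**The plan's own figure.** Follow-up = 112 − 84 = 28 days = 4 × 7. This agrees with the stated 4 weeks, so the visit schedule is consistent with itself. The mismatch is with the 30-day window.

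**Nominal case.** Window end = 84 + 30 = Day 114. Shortfall at a Day 112 call = 114 − 112 = 2 days.

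**Across the permitted call days, last dose on Day 84**

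| Call day | Days since last dose | Shortfall against 30 days |
|---|---|---|
| 108 | 24 | 6 |
| 109 | 25 | 5 |
| 110 | 26 | 4 |
| 111 | 27 | 3 |
| 112 | 28 | 2 |
| 113 | 29 | 1 |
| 114 | 30 | 0 |
| 115 | 31 | none |
| 116 | 32 | none |

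Six of the nine permitted days, including the target day, miss the end of the window. This is a count of days, not a probability.

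**If Visit 6 is counted from the actual last dose.** At last dose + 28 ± 4, follow-up is again 24 to 32 days, so the shortfall is 30 − 24 = 6 days at one end and 30 − 32 = −2 (covered) at the other.

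**Sensitivity to the last-dose day**

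- Latest last dose fully covered = call day − 30: Day 82 for a Day 112 call, Day 78 for a Day 108 call.
- Last dose on Day 83 (the day before Visit 5): the window ends on Day 113, a Day 112 call is 1 day short, and follow-up ranges from 108 − 83 = 25 to 116 − 83 = 33 days.
- Last dose moving with Visit 5 to Day 88, with Visit 6 still at Day 112 ± 4 (an assumption; the text does not say this): the window ends on Day 118. The latest permitted call gives 116 − 88 = 28 days, so no permitted call covers the window. The largest shortfall is 118 − 108 = 10 days.

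**Whether anything else closes the gap.** The follow-to-resolution rule covers events already present at a visit, not new ones that start after the final call. The exit interview has no fixed day, is run outside the site, and is not described as collecting AEs. Footnote 9 has no end date. Nothing in the available text ties Visit 6 to the actual last application.

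**The case against.** The best reply is that a recording window is not a contact schedule. A rule to record events for 30 days and a last planned call at Day 112 ± 4 can both be obeyed: calls on Days 114 to 116 cover the window, and spontaneous reports after an earlier call can still be recorded. That is right, and it is why the point is only that the schedule does not assure the window. Spontaneous reporting is not scheduled enquiry, however, and the available text does not say how reports after Visit 6 are handled.

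Second, the available text stops at the Schedule of Assessments. Its footnote 1 refers to a Section 5.5.1, so a fuller protocol body exists and may contain a 30-day contact or reporting rule. This limits the finding to the synopsis and schedule. If such a rule exists, these two parts should still be brought into line with it.

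Third, Day 84 is inferred. With Day 83 the nominal shortfall is 1 day rather than 2, which changes the size but not the conclusion. The 10-day figure needs a late Visit 5, dosing extended to match, and an early Visit 6; it is an outer bound and should carry little weight.

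Fourth, the consequence is small. The study is descriptive with no comparator, so uneven follow-up cannot bias a comparison between arms. Two days out of 114 is under 2% (2/114 = 1.8%). A subject who stops early and keeps the Day 112 call is covered beyond 30 days. All of this stands and keeps the point modest.

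**Conclusion.** The point holds as an inconsistency between the stated AE window and the scheduled contacts. The nominal shortfall is 2 of 30 days. With the last dose on Day 84, it runs from 6 days to none across the permitted call days. This rests on the last dose falling at about Day 84 and on the synopsis and schedule being the governing text. It should be corrected because it affects data collection for the primary objective, but it does not threaten the study's conclusions.

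**What to change.** Reconcile the AE window with the schedule in one of two ways.

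1. **Move the call.** Time the existing Visit 6 call from the actual last application, so that it cannot fall before the end of the stated window. If no early tolerance is allowed, the earliest call is at last dose + 30 days (Day 114 for a Day 84 last dose), 2 days later than the present target. If the ± 4 days are kept, the target has to be at least last dose + 34 days (84 + 34 = Day 118), 6 days later than now. The edits are the 4-week follow-up wording and the Day 112 entry in Study Design and Duration, the Day 112 column of Table 2, and footnote 2.
2. **Restate the window.** End the AE window at the Day 112 contact and report each subject's actual post-dose follow-up days with the AE tables. This changes one sentence in Adverse Event Coding and adds one reported variable. The window then varies by subject (24 to 32 days for a Day 84 last dose), so the unevenness is disclosed rather than removed, and at the nominal schedule the stated window is 2 days shorter.

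The first option keeps the 30-day commitment and is preferable if that length is intended. Neither option adds a visit. In either case, state how AEs reported spontaneously after Visit 6 are handled.
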